8.1.2 Leukapheresis and Collection of Quiescent APCs

Leukapheresis and collection of blood cells to generate sipuleucel-T is performed at the facility contracted by the manufacturer Dendreon and is analogous to that for autologous blood transfusions. Briefly, subjects undergo a standard 1.5 to 2.0 blood volume leukapheresis to harvest peripheral blood mononuclear cells (PBMCs; primarily lymphocytes and monocytes). Prior mobilization with a colony-stimulating factor is not performed. Immediately after collection, the leukapheresis product is transported to a regional manufacturing facility

8.1.3 Quality Testing

Quality control (QC) testing is performed at several time points during the manufacturing process and on samples of the final product. If the final product passes all required release tests, an approval to infuse the product (Cell Product Disposition Form) is faxed to the infusion center. If a cell product does not meet Dendreon quality specifications, Dendreon will contact the infusion center by telephone and by fax.

Dendreon will provide instructions for product return or destruction of cell products that are not approved or not infused.

8.1.4 Storage and Time Limitations

The infusion of Sipuleucel-T must begin prior to the expiration time indicated on the product label. Expired cell products must not be infused.

8.1.5 Administration

The administration of Sipuleucel-T is performed in the City of Hope infusion clinic. Subjects are premedicated with acetaminophen and an antihistamine such as diphenhydramine prior to the infusion. After the site receives the Cell Product Disposition Form indicating the cell product is approved, the infusion is administered over approximately 60 minutes through an intravenous (IV) line suitable for blood transfusion (without a cell filter). Subjects are observed for at least 30 minutes following the infusion.

8.1.6 Toxicity

The safety evaluation of Sipuleucel-T is based on 601 prostate cancer patients in the Sipuleucel-T group who underwent at least 1 leukapheresis procedure in four randomized, controlled clinical trials. The control was non-activated autologous peripheral blood mononuclear cells.

Almost all (98.3%) patients in the Sipuleucel-T group and 96.0% in the control group reported an adverse event. The most common adverse events, reported in patients in the Sipuleucel-T group at a rate $\geq 15\%$, were chills, fatigue, fever, back pain, nausea, joint ache, and headache. In 67.4% of patients in the Sipuleucel-T group, these adverse events were mild or moderate in severity. Severe (Grade 3) and life-threatening (Grade 4) adverse events were reported in 23.6% and 4.0% of patients in the Sipuleucel-T group compared with 25.1% and 3.3% of patients in the control group. Fatal (Grade 5) adverse events were reported in 3.3% of patients in the Sipuleucel-T group compared with 3.6% of patients in the control group. The most common ($\geq 2\%$) Grade 3-5 adverse events reported in the Sipuleucel-T group were back pain and chills.

Serious adverse events were reported in 24.0% of patients in the Sipuleucel-T group and 25.1% of patients in the control group. Serious adverse events in the Sipuleucel-T group included acute infusion reactions, cerebrovascular events, and single case reports of eosinophilia, rhabdomyolysis, myasthenia gravis, myositis, and tumor flare.

Sipuleucel-T was discontinued in 1.5% of patients in Study 1 due to adverse events. Some patients who required central venous catheters for treatment with PROVENGE developed infections, including sepsis. A small number of these patients discontinued treatment as a result. Monitoring for infectious sequelae in patients with central venous catheters is recommended.

Each dose of Sipuleucel-T requires a standard leukapheresis procedure approximately 3 days prior to the infusion. Adverse events that were reported ≤ 1 day following a leukapheresis procedure in $\geq 5\%$ of patients in controlled clinical trials included citrate toxicity (14.2%), oral paresthesia (12.6%), paresthesia (11.4%), and fatigue (8.3%).

Table 1 provides the frequency and severity of adverse events reported in $\geq 5\%$ of patients in the Sipuleucel-T group of randomized, controlled trials of men with prostate cancer.

Table 1 Incidence of Adverse Events Occurring in $\geq 5\%$ of Patients Randomized to Sipuleucel-T

	Sipuleucel-T (N = 601)		Control* (N = 303)	
	All Grades n (%)	Grade 3-5 n (%)	All Grades n (%)	Grade 3-5 n (%)
Any Adverse Event	591 (98.3)	186 (30.9)	291 (96.0)	97 (32.0)
Chills	319 (53.1)	13 (2.2)	33 (10.9)	0 (0.0)
Fatigue	247 (41.1)	6 (1.0)	105 (34.7)	4 (1.3)
Fever	188 (31.3)	6 (1.0)	29 (9.6)	3 (1.0)
Back pain	178 (29.6)	18 (3.0)	87 (28.7)	9 (3.0)
Nausea	129 (21.5)	3 (0.5)	45 (14.9)	0 (0.0)
Joint ache	118 (19.6)	11 (1.8)	62 (20.5)	5 (1.7)
Headache	109 (18.1)	4 (0.7)	20 (6.6)	0 (0.0)
Citrate toxicity	89 (14.8)	0 (0.0)	43 (14.2)	0 (0.0)
Paresthesia	85 (14.1)	1 (0.2)	43 (14.2)	0 (0.0)
Vomiting	80 (13.3)	2 (0.3)	23 (7.6)	0 (0.0)
Anemia	75 (12.5)	11 (1.8)	34 (11.2)	7 (2.3)
Constipation	74 (12.3)	1 (0.2)	40 (13.2)	3 (1.0)
Pain	74 (12.3)	7 (1.2)	20 (6.6)	3 (1.0)
Paresthesia oral	74 (12.3)	0 (0.0)	43 (14.2)	0 (0.0)
Pain in extremity	73 (12.1)	5 (0.8)	40 (13.2)	1 (0.3)
Dizziness	71 (11.8)	2 (0.3)	34 (11.2)	0 (0.0)
Muscle ache	71 (11.8)	3 (0.5)	17 (5.6)	0 (0.0)
Asthenia	65 (10.8)	6 (1.0)	20 (6.6)	2 (0.7)
Diarrhea	60 (10.0)	1 (0.2)	34 (11.2)	3 (1.0)
Influenza-like illness	58 (9.7)	0 (0.0)	11 (3.6)	0 (0.0)
Musculoskeletal pain	54 (9.0)	3 (0.5)	31 (10.2)	3 (1.0)
Dyspnea	52 (8.7)	11 (1.8)	14 (4.6)	3 (1.0)
Edema peripheral	50 (8.3)	1 (0.2)	31 (10.2)	1 (0.3)
Hot flush	49 (8.2)	2 (0.3)	29 (9.6)	1 (0.3)
Hematuria	46 (7.7)	6 (1.0)	18 (5.9)	3 (1.0)
Muscle spasms	46 (7.7)	2 (0.3)	17 (5.6)	0 (0.0)

8.2 Radiation therapy

8.2.1 Treatment Plan:

In patients assigned to Arm B one metastatic site will be selected for radiation based primarily on the safety of radiation in that location. Radiation to bone metastases in L3-S5, pelvis and femurs will be excluded provided that patients have other areas of metastases. Patients who have metastases only in the above locations (L3-S5, pelvis and femurs) will be allowed provided that they have normal WBC and they will not receive radiation to more than 20% of the bone marrow. The gross tumor volume (GTV) will be defined as the radiological dimensions of the lesion as identified by CT and/or MRI. The planning tumor volume (PTV) is defined as the GTV plus 1 cm. For lesions that move with respiration (Rib and lung parenchymal lesions for example) CT simulation will be performed at inspiration and expiration to define lesion position during the respiratory cycle. The GTV will be defined based on lesion position during the respiratory cycle. Radiation treatment fields will be arranged to minimize dose to the marrow and whole body. Conventional AP/PA technique will be used. Field will be limited to 10 by 10 cm. Patients will be treated with 300 cGy/day to 3000 cGy; Approximately 7 days after completion of radiation therapy, patients will begin therapy with Sipuleucel-T autologous vaccine.

8.2.2 Toxicity:

The risks of radiation therapy depend on the part of the body being treated. These side effects are generally mild and expected to resolve 1-2 weeks after radiation is completed:

- fatigue,
- anorexia
- gastroesophageal reflux
- diarrhea
- nausea
- dysuria
- urinary frequency
- pain flare
- skin rash,
- neutropenia,
- thrombocytopenia,
- anemia

Long term effects of radiation also depend on the specific location being treated and include:

- pneumonitis
- cystitis
- hematuria
- secondary malignancy
- chronic diarrhea
- bowel perforation

9.0 Correlative/Special Studies

Blood collection must be scheduled Monday to Thursday to allow for overnight shipping to be received by Friday. Specimens will be labeled with the subjects research participant number.

9.1 Blood Collection

ALL SUBJECTS

100ml total whole blood (90mL collected in sodium heparin vacutainer tubes and 10mL collected in no-anticoagulant vacutaine tubes- from Becton Dickinson) collected at each time point specified in the study calendar (pre-study, and during weeks 4, 12, 24, 36, 48, and 60) will be sent to:

Send the sample(s) **priority overnight** via FedEx Next Day to:

Dendreon Corporation

Attention: Clinical Immunology

[name]

[contact]

ONLY SUBJECTS RECEIVING RADIATION AT CITY OF HOPE

10ml of the whole blood in the BD Vacutainer CPT tube (with Heparin) will collected at baseline (week 0) and at week 4 after radiation to be sent to the laboratory of [name] within 4 hours of collection to avoid degradation of the phosphomoieties (i.e., pSTAT3) assessed in this protocol. CPT tubes will be centrifuged at 1800g (approximately 2800 rpm on a Sorvall RT6000 centrifuge) for 20 min. at room temperature. After centrifugation, plasma in the CPT tubes will be gently pipetted against the gel plug to dislodge cells stuck to the top of the gel. The cell suspension will be transferred to a 50 mL conical polypropylene tube. cRPMI will be added to a total of 40 mL. A 10 mL aliquot of cell suspension for counting will be removed. The 50 mL tubes will then be centrifuged at 250g for seven minutes at room temperature. When centrifugation is complete, the supernatant will be aspirated. PMBCs will be either cryopreserved or used fresh.

9.2 Immune Assays

9.2.1 Cellular immune response assays – Elispot

Antigen-specific memory T cell responses are assayed by means of a IFN γ ELISPOT assay. PVDF ELISPOT (enzyme-linked immunoSPOT) plates (Millipore) are coated with an anti-IFN γ monoclonal antibody (mAb) (clone D1K, MabTech) overnight, after which time plates are blocked and washed with phosphate-buffered saline/Tween (PBST). Cryopreserved PBMC, thawed and rested overnight in medium are then plated in triplicate at 3×10^5 PBMC/well in a total volume of 200 μ L/well with either medium alone or with medium containing antigen (PA2024: PAP-GMCSF fusion protein, PAP or PHA – Phytohaemagglutinin, an assay control). Plates are then incubated for 40-48 hrs after which time plates are washed then incubated with Streptavidin conjugated anti-

IFN γ mAb (clone B6-1, MabTech). After incubation plates are further washed with PBST and then incubated biotin conjugated with alkaline peroxidase for a further hour. Afterwards plates are then washed with PBST and then incubated with a substrate, BCIP (5-Bromo-4-chloro-3-indolyl phosphate) to visualize IFN γ secreting cells. ELISPOT data are presented as the median of triplicates with background (PBMCs incubated with media) IFN γ spots subtracted.

9.2.2 Cellular immune response assays – Proliferation

Antigen-specific T cell proliferation to PA2024, PAP and PHA are assayed by means a standard tritiated thymidine (^3H -thymidine) incorporation assay using round bottom 96 well tissue culture plates. Cryopreserved PBMC, thawed and rested overnight in medium are then plated in triplicate at 1×10^5 PBMC/well in a total volume of $200 \mu\text{L}$ /well with either medium alone or with medium containing antigen (PA2024: PAP-GMCSF fusion protein, PAP or PHA). Plates are incubated for 5 days, after which the wells are pulsed with $0.5 \mu\text{Ci}$ of ^3H -thymidine overnight, and the amount of ^3H -thymidine incorporation into the nucleus is quantified by means of a β -radiation counter with the degree of proliferation expressed as a stimulation index (SI), defined as ^3H -thymidine incorporation in the presence of antigen divided by ^3H -thymidine incorporation with media alone.

9.2.3 Humoral response assays

Antibody responses against PA2024 and PAP are determined by means of standard antibody ELISA (enzyme-linked immunosorbent assay). 96 well flat bottomed plates are coated with either PA2024, PAP or Tetanus (an assay control, and measure of immunocompetence) overnight, after which time plates are blocked with PBS/casein and then washed with PBST. Serially diluted serum is then added in duplicate to each set of plates and incubated at room temperature for 2 hours, after which time plates are washed with PBST and then incubated with a mixture of anti-IgM and anti-IgG (Jackson ImmunoResearch) for an hour. After this time plates are washed again with PBST and then incubated for an hour with horse radish phosphatase conjugated anti IgG+anti-IgM. Plates were further washed with PBST and O-phenylenediamine dihydrochloride substrate (Sigma) was then added for 15 minutes after which the developing reaction was stopped by the addition of $50 \mu\text{l}$ /well of 2N HCL (Sigma). Plates were read on a Synergy HT spectrophotometer (BioTEK) at 492 nm and the endpoint titer was determined as being the last dilution of serum that yielded an O.D. reading equivalent to assay background.

9.3 Analysis of PBMCs

9.3.1 Analysis of pSTAT3 in PBMCs

Analysis of pSTAT3 will be conducted through previously reported techniques (Kortylewski *et al. Nature Med* 2007). PBMCs will be immersed in a mixture of PBS, 2% FCS and 0.1% (wt/vol) sodium azide with Fc III/IIR-specific antibody to block nonspecific binding and stained the cells with different combinations of fluorochrome-coupled antibodies to CD4, CD14, CD15, CD25, CD33, FoxP3 or HLA-DR as well as 7AAD for dead cell exclusion (BD Biosciences). We collected fluorescence data on

FACSCalibur (Beckton Dickinson) and analyzed them using FlowJo software (Tree Star). This method has been previously published by Chalmin et al.11

9.3.2 Determination of serum cytokine and chemokine levels

Serum levels of proinflammatory cytokines and chemokines induced by radiation therapy will be ascertained through the Luminex Protein Assay (Invitrogen) as per manufacturer instructions.

9.3.3 Detection of circulating mtDNA and other TLR9 ligands

Levels of TLR9 ligands (e.g. mtDNAs), will be assessed using quantitative qPCR as described by Zhang et al.(Blood 2013). Briefly, DNA will be isolated from plasma samples using QIAamp DNA Mini kit (Qiagen). The presence of human mitochondrial genes, such as cytochrome B, cytochrome C oxidase subunit III and NADH dehydrogenase, will be detected by qPCR using specific pairs of primers on CFX96 thermocycler (Biorad).

10.0 Study Calendar

Table 1 Schedule of Events (time scale in weeks)

ARM B #

	Week ^f													Off Study Visit ⁱ
	Pre-Study *	1	2	3	4	5	6	7	8	9	10	11	12 ^b	
Radiation therapy # (Arm B only)		X	X											
Sipuleucel-T collection				X		X		X						
Sipuleucel-T infusion					X		X		X					
Informed consent	X													
Demographics	X													
Medical history	X													X
Physical exam	X				X		X		X				X	X
Performance Status	X				X		X		X				X	X
CBC w/diff, plts	X	X	X	X		X		X					X	Xe
Serum chemistry ^a	X				X		X		X				X	Xe
PSA	X				X								X	Xe
Testosterone	X												X	
EKG (as indicated)	X													
CXR (if no CT chest done)	X												X ^c	X ^c
Radiologic evaluation(bone scan, CT (Chest ^g) Abd/pelvis ^g	X												X ^c	X ^c
Tumor measurements	X												X ^c	X ^c
Adverse event evaluation					X		X		X				X ^c	X ^c
Immune Assays	X				X								X ^d	
Analysis of PBMCs ^h	X				X									

Patients on ARM A will not undergo radiation therapy, otherwise they will follow the same schedule as ARM B beginning on week 3

* Prestudy tests should be performed within 28 days of registration

- Albumin, alkaline phosphatase, total bilirubin, bicarbonate, BUN, calcium, chloride, creatinine, glucose, LDH, phosphorus, potassium, total protein, SGOT[AST], SGPT[ALT], sodium.
- and every 12 weeks thereafter until off the study

-
- c. after week 12 radiologic evaluation and tumor measurement will be done at the discretion of treating physician
 - d. after week 12 Immune Assays will be performed at following time intervals : week 24, 36, 48, 60
 - e. Off study visit laboratory tests will be performed at the discretion of treating physician
 - f. this protocol allows for flexibility of suggested timing of visits and tests : +/- 1 week during first 8 weeks of study and +/- 2 weeks thereafter
 - g. Chest CT is optional. If not done it can be replaced with PA and LAT Chest XRay. MRI of the abdomen and pelvis can be used instead of CT
 - h. City of Hope subjects who receive radiation only
 - i. done approximately 30 days post study completion

11.0 Endpoint Evaluation Criteria/Measurement of Effect

11.1 Measurability of lesions

a. **Measurable disease:** Lesions that can be accurately measured in at least one dimension by 1) medical photograph (skin or oral lesion), palpation, plain x-ray, CT, MRI or other conventional technique with longest diameter 2 cm or greater in the axial plane (bone lesions not included), or 2) spiral CT with longest diameter 1 cm or greater. Ultrasound is suitable only for superficial disease (superficial palpable nodes, subcutaneous lesions, thyroid nodules).

Conventional CT and MRI should be performed with cuts of 10 mm or less in slice thickness contiguously. Spiral CT should be performed using a 5 mm contiguous reconstruction algorithm.

b. **Non-measurable disease:** All other lesions including lesions too small to be considered measurable, pleural or pericardial effusions, ascites, bone disease, inflammatory breast disease, leptomeningeal disease, lymphangitis, pulmonitis, abdominal masses not confirmed and followed by imaging techniques, cystic lesions or disease documented by indirect evidence only (e.g., by lab values), previously radiated lesions that have not progressed.

11.2 Objective status

Objective Status is to be recorded at baseline, at week 12 (or at the time of disease progression if it happened earlier than 12 weeks) All measurable lesions up to a maximum of 5 lesions per organ and 10 lesions in total, representative of all involved organs, should be identified as target lesions at baseline. All measurable lesions not identified as target lesions are non-target lesions and are included as non-measurable disease. Measurements must be provided for target measurable lesions, while presence or absence must be noted for non-target measurable and non-measurable disease.

- a. **Complete Response (CR):** Complete disappearance of all measurable and non-measurable disease. No new lesions. No disease related symptoms, normalization of disease-related abnormal lab values. Normalization of PSA marker to ≤ 0.2 in patients who had prior prostatectomy. In patients who had primary radiation therapy to prostate gland PSA decrease to $< \text{nadir} + 2$. All disease must be assessed using the same technique as baseline.
- b. **Partial Response (PR):** Radiographic PR applies only to patients with at least one measurable lesion. Greater than or equal to 30% decrease under baseline of the sum of longest diameters of all target measurable lesions. No unequivocal progression of non-measurable disease. No new lesions. All target measurable lesions must be assessed using the same techniques as baseline. PSA PR refers to PSA decline by $> 50\%$ from baseline and confirmed at least 3 weeks later.
- c. **Stable:** Does not qualify for CR, PR, Progression or Symptomatic Deterioration. All target measurable lesions must be assessed using the same techniques as baseline.
- d. **Progression:** One or more of the following must occur: 20% increase in the sum of longest diameters of target measurable lesions over smallest sum observed (over baseline if no decrease during therapy) using the same techniques as baseline. Unequivocal progression of non-measurable disease in the opinion of the treating physician (an explanation must be provided). Appearance of any new lesion/site. PSA increase by 25 % from baseline or nadir (whichever was smaller) and by ≥ 2 ng/mL at 12 weeks. Death due to disease without prior documentation of progression and without symptomatic deterioration.

- e. **Symptomatic deterioration:** Global deterioration of health status requiring discontinuation of treatment without objective evidence of progression. Efforts should be made to obtain objective evidence of progression after discontinuation.
- f. **Assessment inadequate, objective status unknown:** Progression or symptomatic deterioration has not been documented, and one or more target measurable lesions have not been assessed or inconsistent assessment methods were used.
- g. **Objective status notes:**
 1. Non-measurable and non-target measurable disease do not affect objective status except in determination of CR (must be absent--a patient who otherwise has a CR, but who has non-measurable or non-target measurable disease present or not assessed, will be classified as having a PR), and in determination of progression (if new sites of disease develop or if unequivocal progression occurs in the opinion of the treating physician).
 2. An objective status of PR or stable cannot follow one of CR. Stable can follow PR only in the rare case that tumor increases too little to qualify as progression, but enough that a previously documented 30% decrease no longer holds.
 3. In cases for which initial flare reaction is possible (hypercalcemia, increased bone pain, erythema of skin lesions), objective status is not progression unless either symptoms persist beyond 4 weeks or there is additional evidence of progression.
 4. Lesions that appear to increase in size due to presence of necrotic tissue will not be considered to have progressed.
 5. For bone disease documented on bone scan only, increased uptake does not constitute unequivocal progression.
 6. Appearance or worsening of pleural effusions does not constitute unequivocal progression unless cytologically proven of neoplastic origin.
 7. If CR determination depends on a lesion for which the status is unclear by the required tests, it is recommended the residual lesion be investigated with biopsy or fine needle aspirate.

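### Section 11.2 gives no rule for the lesion irradiated in Arm B, so its local shrinkage alone can meet radiographic PR in that arm only, and objective 3 does not say whether that should count

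*Combined protocol and SAP*

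**What the plan says.** Secondary objective 3 (section 1.0) concerns the effect of radiation to one metastasis on the radiographic response rate. Section 11.2 takes as targets "All measurable lesions up to a maximum of 5 lesions per organ and 10 lesions in total", chosen at baseline. PR requires "Greater than or equal to 30% decrease under baseline of the sum of longest diameters of all target measurable lesions", with no new lesions and no unequivocal progression of non-measurable disease. Objective status is recorded at baseline and at week 12, or at progression if that is earlier.

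Under the section 10.0 calendar, "Prestudy tests should be performed within 28 days of registration". Section 4.3 places registration before treatment starts, and radiation is in weeks 1-2, in Arm B only.

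The nearest rule is in section 11.1, which lists among non-measurable disease "previously radiated lesions that have not progressed". Section 11.1 also treats bone disease as non-measurable ("bone lesions not included"), and section 3.2 excludes liver metastases. Section 3.1 accepts soft-tissue metastases, and section 8.2.1 gives lung parenchymal lesions as an example of a site that may be irradiated.

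**The concern.** The irradiated lesion is untreated when targets are chosen, so on its plain wording the section 11.1 clause does not reach it. At week 12 a reader might apply the clause anyway, so the three participating sites could score the same scan differently. The notes to section 11.2 and section 13.3 are silent. Followed as written, the plan counts the irradiated lesion like any other target.

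Arm A has no radiation, so a PR produced by direct in-field shrinkage can arise only in Arm B. Section 2.1 states the hypothesis that irradiating one site enhances the immune response to Sipuleucel-T. A higher response rate in Arm B could be read as support for this when it is only the local effect of radiation. Sections 2.1 and 2.4 also report that Sipuleucel-T produced no significant objective responses in the Phase III trial, although section 2.4 mentions some regressions in early trials. If Arm A has few responses, a small number of in-field PRs could dominate the comparison.

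**Working it through.** The plan gives no rate, power or significance level for radiographic response, so there is no figure to reproduce. The only input from the documents is the 30% threshold in section 11.2.

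**When local shrinkage is enough.** Let f be the irradiated lesion's share of the baseline target sum, s its fractional shrinkage, and g the net fractional growth of the other targets. The relative change in the sum is -s·f + g·(1-f). PR requires this to be -0.30 or lower, so

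s ≥ (0.30 + g(1-f)) / f.

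Since s cannot exceed 1, this is possible only if f ≥ (0.30 + g)/(1 + g), which is 0.300 at g = 0, 0.364 at g = 0.10 and 0.417 at g = 0.20. The values of f and g below are assumed; the documents give none.

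| Share f | Shrinkage needed, g = 0 | g = 10% | g = 20% |
|---|---|---|---|
| 100% | 30% | 30% | 30% |
| 75% | 40% | 43% | 47% |
| 50% | 60% | 70% | 80% |
| 40% | 75% | 90% | not possible |
| 30% | 100% | not possible | not possible |

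At f = 100% there are no other targets, so g has no effect. With equal-sized targets and g = 0, the shrinkage needed is 30% for one target, 60% for two and 90% for three. With four it would be 120%, so PR from one lesion is impossible.

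Check at f = 50%, g = 20%: take a baseline of 50 + 50 = 100. After 80% in-field shrinkage and 20% growth elsewhere, the sum is 50 × 0.20 + 50 × 1.20 = 70, exactly a 30% fall. The patient meets the size criterion although every unirradiated target may have grown.

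**Masked progression.** Section 11.2 calls a 20% increase in the sum progression. If the irradiated lesion goes from 50 to 10 and the others from 50 to 75, the sum falls from 100 to 85. The other lesions have grown by 25/50 = 50%, yet the sum criterion for progression is not met.

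**Effect on the comparison (illustration only).** Assume m evaluable patients per arm, no responses in Arm A, and x in-field PRs in Arm B. The one-sided Fisher p-value is C(m,x)/C(2m,x).

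| x | m = 6 | m = 12 | m = 25 |
|---|---|---|---|
| 2 | 15/66 = 0.227 | 66/276 = 0.239 | 300/1225 = 0.245 |
| 3 | 20/220 = 0.091 | 220/2024 = 0.109 | 2300/19600 = 0.117 |

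Section 13.3 uses a one-sided 0.20 level for the antibody comparison and sets none for radiographic response. By that borrowed yardstick, two in-field PRs fall short and three do not.

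**The case against.** The strongest objection is that response to the whole regimen is a legitimate endpoint. Objective 3 asks what radiation does to the response rate, and section 13.1 speaks of response to Sipuleucel-T with or without radiation. On that reading in-field shrinkage is part of the effect. The enhancement hypothesis is about immune response, which objective 1 measures with assays, and no section states an out-of-field radiographic objective. This stands in part. A reader might infer that the Arm B rate is simply biased, but the documents do not support that without a condition: it is a bias if objective 3 means response to Sipuleucel-T, and not if it means response to the regimen. The text does not say which.

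Three further limits stand. The arithmetic shows what is possible, not how often it happens; many irradiated sites may be bone, which cannot be a target. Other targets in the field raise the same question, since "Field will be limited to 10 by 10 cm", but section 8.2.1 also sets the planning volume at the lesion plus 1 cm and minimises dose elsewhere, so this should not be assumed typical. Last, a reader might see a second route to response in the section 11.2 note that classes an otherwise complete responder with residual non-target or non-measurable disease as PR. It adds none: if every target disappears the sum has fallen by 100% and PR is already met on size, and CR also carries symptom, laboratory and PSA conditions that in-field disappearance does not satisfy.

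It can also be said that Arm B could be rescored at analysis without the irradiated lesion, because the measurements will exist. That is true for Arm B. But removing a lesion in one arm only makes the arms unlike: an Arm B patient whose only target was irradiated would become non-evaluable, while his Arm A counterpart would stay in. A matching Arm A site has to be named before assignment is known.

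**Conclusion.** The point holds. As written, section 11.2 lets direct shrinkage of the irradiated lesion produce a radiographic PR by itself, in Arm B only. This requires the lesion to be a measurable non-bone target with at least 30% of the baseline sum if the other targets are unchanged, or more if they grow, and no new lesions or unequivocal progression. The comparison for objective 3 therefore cannot distinguish a local radiation effect from an enhanced response to Sipuleucel-T, and the intended reading is not stated.

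The size in practice is unknown, because the documents do not give the share of patients with such a lesion. The consequence is confined to a secondary, exploratory and unpowered endpoint that section 13.3 intends to inform future studies. The primary feasibility endpoint, the stopping rules and the antibody comparison are untouched. It should be fixed because the remedy is cheap and its key element, naming the site in both arms, has to be in place before randomisation.

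**What to change.** - In section 11.1, state that the clause on previously radiated lesions means radiated before baseline.
- At registration, before randomisation and in both arms, record the one site that is or would be irradiated.
- For objective 3, report radiographic response two ways in both arms: on all target lesions (the whole regimen), and on target lesions other than the designated site (out-of-field response). State that the second addresses enhancement of Sipuleucel-T. Patients with no other target are not evaluable in it.
- In the out-of-field version, apply the sum-based progression criterion to the same lesions, so that in-field shrinkage does not mask growth elsewhere.
- Keep the designated-site analysis as the between-arm comparison. Report the number of Arm B site changes and, as a sensitivity analysis, the Arm B result without the lesion actually treated and any other target found in its field.

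The cost is protocol wording, one registration entry and re-summing of measurements already required. No new scans are needed, and neither treatment nor site selection changes. The downsides are a brief site nomination in Arm A that would not otherwise be made, and fewer evaluable patients in the out-of-field version; the all-lesion result keeps them.
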